5.5 Presentation Conventions

For all parameters, where applicable:

• n: no decimal place,

LEVI-04-21-02 Statistical Analysis Plan	Version: Final 3.0
Date: 18-Mar-2024	Page 29 of 34

• CV% and CV% geometric mean will be displayed to one decimal place,

Parameters that are reported or derived at a fixed number of decimal points (e.g., vital sign measurements, including body mass index (BMI), clinical laboratory test parameters, and plasma drug concentrations), will be reported as follows:

- Mean, median, and first and third quartiles will be displayed to one more decimal than the maximum number of decimal places reported for the original data,
- SD will be reported to two more decimal places than the maximum number of decimal places reported for the original data,
- Minimum and maximum will be reported to the maximum number of decimal places reported for the original data.

5.5.1 Significant Figures

When descriptive statistics are to be presented to a specific number of significant figures, the following conventions will be utilized:

- Results of "0" will be displayed as "0".
- Results that cannot be displayed to the exact specified number of significant figures (in Section 3.5) without the use of scientific notation will be displayed using the maximum number of significant figures that is less than the specified number of significant figures. E.g., "1000" and "1295" cannot be displayed to three significant figures without the use of scientific notation, so "1000" and "1300" would be presented, respectively.
- All other results will be displayed to the specified number of significant figures in Section 3.5. Examples of results displayed to three significant figures are presented below:

Original Result	Presentation Result
	(3 Significant Figures)
12.34	12.3
0.01234	0.0123
0.12	0.120
10	10.0
1234	1230

LEVI-04-21-02 Statistical Analysis Plan	Version: Final 3.0
Date: 18-Mar-2024	Page 30 of 34

6. CHANGES FROM THE PROTOCOL

The secondary objective "To evaluate the proportion of responders based on various levels of reduced pain in participants receiving LEVI-04 (multiple doses) compared to placebo" was overly specific with regards to the endpoints associated with it. That is, not all associated endpoints are response rates. However, all the endpoints are measures of pain, so the objective was modified to: "To evaluate the efficacy of LEVI-04 (multiple doses) compared to placebo in reducing pain".

The protocol specifies that descriptive statistics will be provided for physical examinations. Results for individual body systems are not collected. Any abnormalities are recorded as medical history or adverse events.

Analyses associated with exploratory endpoint "to explore associations between imaging biomarkers and pain severity" will not be conducted at this time. These analyses may be generated at a later date.

The protocol specifies that the daily average amount of rescue medication usage and the proportion of days on rescue medication while on treatment will be calculated by dividing by the number of days on study treatment. If participants do not have any missing diary entries and complete the study, then using the number of days on study treatment for the denominator for these parameters will provide reasonable estimates. However, participants may not complete the study or provide responses to the rescue medication usage for all days. For these instances, rescue medication usage and the proportion of days on rescue medication would be underestimated if using the number of days on study treatment as the denominator as it would assume zero usage on those unknown days. In order to provide more accurate estimates for these two parameters, the denominator will only include those study days for which the required usage information is known for the given parameter.

7. INTERIM ANALYSIS

An interim analysis (IA) will be conducted on the first 208 randomized participants in the study. The interim analysis will be performed once all 208 participants have completed the Week 5 visit or have discontinued prior to Week 5. Based on the IA's conditional power analysis, the study will continue as planned with a total of 416 participants randomized, or with an increase of up to 208 participants (an additional 50%) up to a total of 624 participants. Conditional power calculations will be performed using two alternative methodologies:

1. Multiple imputations will be utilized to impute missing data. The Week 17 effect size will be determined for each imputation. The conditional power will be calculated based on these multiple imputations interim Week 17 effect sizes. The Week 17 effect size for the

LEVI-04-21-02 Statistical Analysis Plan	Version: Final 3.0
Date: 18-Mar-2024	Page 31 of 34

- post-interim participants will be assumed to be from the same distribution as its associated Week 17 effect size estimate from the interim participants.
- 2. Multiple imputations will be utilized to impute missing data. The Week 5 effect size will be determined for each imputation. The conditional power will be calculated based on these multiple imputations interim Week 5 effect sizes. The Week 5 effect size for the post-interim participants will be assumed to be from the same distribution as its associated Week 5 effect size from the interim participants

A single set of one hundred imputations will be determined and utilized for both methods above.

The IA summary will be shared with the IA independent statistician. Below is the mock summary of the IA:

LEVI-04-21-02 Statistical Analysis Plan	Version: Final 3.0
Date: 18-Mar-2024	Page 32 of 34

Page 1 of 1 DDMMMYYYY **DRAFT** program.sas

Levicept Ltd.: Protocol LEVI-04_21_02 Table 1 Interim Analysis

Summary of Mean Change from Baseline in WOMAC Pain Subscale Score and Associated Conditional Power Intent-to-Treat Analysis Set – Multiple Imputations

	0.3 mg/kg (N=xx)	1.0 mg/kg (N=xx)	2.0 mg/kg (N=xx)	Placebo (N=xx)
Method 1: Change from Baseline to Week 17	1	1		
n	XX	XX	xx	XX
LS Mean (SE) ^a	xx (xx.x)	xx (xx.x)	xx (xx.x)	xx (xx.x)
LS Mean Difference (SE) ^a	xx (xx.x)	xx (xx.x)	xx (xx.x)	
Method 2: Change from Baseline to Week 5				
N	XX	xx	xx	xx
LS Mean (SE) ^a	xx (xx.x)	xx (xx.x)	xx (xx.x)	xx (xx.x)
LS Mean Difference (SE) ^a	xx (xx.x)	xx (xx.x)	xx (xx.x)	
Conditional Power ^b	 			
Method 1				
Final planned sample size (N=416)			XX.X	
50% increase in final sample size (N=624)	XX.X			
Method 2				
Final planned sample size (N=416)	xx.x			
50% increase in final sample size (N=624)	XX.X			

- a: From an ANCOVA model with main effect treatment and covariates study center and baseline score with missing scores imputed using multiple imputations methodology. For method 1, participants that are still in study without week 17 data will be considered as missing at random. For both methods 1 and 2, for participants who discontinued due to lack of efficacy of adverse event, imputation will be done using the placebo as the treatment group.
- b: Conditional power is calculated as the probability for at least one of the comparisons against placebo is significant at the Dunnett adjusted type-1 error of 0.xxx per comparison (controlling overall type-1 error at a two-sided 0.05 level), assuming the post-interim effect size comes from the same distribution as its associated interim effect size.

LEVI-04-21-02 Statistical Analysis Plan	Version: Final 3.0
Date: 18-Mar-2024	Page 33 of 34

The two methods of estimating the effect size and consequently, the conditional power could lead to different sample size reassessments. The independent statistician will report the most conservative (largest) sample size in the recommendation to the designated personnel at Levicept. The only recommendation communicated to Levicept will be whether the sample size will need to increase or stay the same.

Conditional Power Calculations

For each of the methods above, conditional power will be calculated as follows:

1. Z_{ii} , i = 1,2.3 will be calculated by transforming the interim p-value of each dose group

comparison to placebo using the inverse normal transformation of the ANOVA t-statistics.

2.
$$\delta_i = Z_{i1} \sqrt{\frac{1}{i} + \frac{1}{i}}$$
, $i = 1,2,3$ is the effect size of the three dose group comparisons to

placebo from the interim participants, which is assumed to be also the effect size of the post-interim participants.

$$\rho_{ij} = \lambda_{i \ j}, \lambda_{i} = \sqrt{\frac{ni1}{ni1 + n01}}$$

LEVI-04-21-02 Statistical Analysis Plan	Version: Final 3.0
Date: 18-Mar-2024	Page 34 of 34

4. Let Λ be a lower triangular matrix from the Cholesky decomposition of Σ .

 X_1 Let $X = (X_2)$ be a three-dimensional vector of independent standard normal random X_3

variables and let
$$\Delta = \frac{\frac{\delta_1}{\sqrt{\frac{1}{n_{12}} + \frac{1}{n_{102}}}}}{\sqrt{\frac{1}{n_{12}} + \frac{1}{n_{02}}}}$$
. Then $\Lambda'X + \Delta = Z_2 = (Z_{2,2})$ is a three-dimensional
$$\frac{\delta_3}{\sqrt{\frac{1}{n_{32}} + \frac{1}{n_{02}}}}$$

vector of normal random variables, with a correlation matrix Σ , representing the test statistics of post-interim participants with the same effect size as the interim participants.

5. Generate 5,000 random vectors of Z_2 .

LEVI-04-21-02 Statistical Analysis Plan	Version: Final 3.0
Date: 18-Mar-2024	Page 35 of 34

For each random vector \mathbb{Z}_2 , calculate:

$$Z=\sqrt{\frac{1}{2}}Z+\sqrt{\frac{1}{2}}Z$$
, $i=1,2,3$, which is the (combination) Z-statistics for the three $i=2$, $i,1=2$, $i,2$

pairwise comparisons at the end of the study. Note that in each of the 5,000 samples, $Z_{i,1}$, i = 1,2,3, is fixed and equals to the interim $Z_{i,1}$ statistic.

In each of the 5,000 simulations, if:

 $(abs(Z_1) > C)$ or $(abs(Z_2) > C)$ or $(abs(Z_3) > C)$ then reject H_0 , where C is the critical value from the two-sided Dunnett test for 3 pairwise comparisons calculated using PROBMC of SAS:

C = PROBMC("DUNNETT2", ., 0.95, ., 3, lam1, lam2, lam3), where lami is as defined in Section 4.11. For equal sample sizes $C \approx 2.349$.

6. The proportion of times that H_0 is rejected is the estimated conditional power.

Note that the application of Dunnett's test to a combination test relies on large sample property of the t-distribution namely the asymptotic distribution is normal. This allows to approximate the correlation matrix among the combination test statistics using the correlation matrix associated with the t-statistics.

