10.1 Sample Size

This study is planned to enroll approximately 416 participants, with a possibility of adding an additional 208 participants pending a conditional power analysis done at the interim analysis (IA). It is assumed that there is a minimum effect of 10 out of 100 in change from baseline in WOMAC pain sub-score for at least one of dose groups compared with placebo, and a standard deviation of 19.2 for change from baseline. Dropout rate is assumed to be 15%, distributed evenly over the study duration of the study. An IA will be conducted when approximately 208 participants have completed the Week 5 visit, and approximately 80 have completed the Week 17 visit. Based on the IA's conditional power analysis, the study will continue as planned with a total of 416 participants randomized, or with an increase of up to 208 participants (an additional 50%) up to a total of 624 participants. The final analysis will be conducted between the three treatment arms and placebo using a simple combination test with weights of 1/2 on the interim Z, and 1/2 on final Z, using a Dunnett's test. Therefore, each comparison will be made at a two-sided 0.0188 level of significance. With this design, the power for a statistically significant difference between at least one active treatment group versus placebo assuming the study will continue to at least the originally planned sample size is:

Effect scenario: treatment mean difference versus placebo			Power with sample size of 416	Increase of sample size to 624 at the IA		
Arm 1	Arm 2	Arm 2	SD=19.2	SD=22	SD=23	SD=24
10	7.5	5	90%	94%	92%	90%
10	5	2.5	88%	92%	89%	86%
10	0	0	86%	91%	88%	85%

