significant (>0.05), then all three comparisons will be considered non-significantly different from placebo. If the lowest adjusted p-value is significant (≤ 0.05), then the associated LEVI-04 dose level will be considered significantly different from placebo. The testing will continue by applying a Dunnett adjustment for two comparisons (the remaining two LEVI-04 dose levels) with placebo. If the lowest adjusted p-value from the two comparison Dunnett adjustment is non-significant, then the remaining two dose levels will be considered non-significantly different from placebo. If the lowest adjusted p-value from the two comparison Dunnett adjustment is significant, then the associated LEVI-04 dose level will also be considered significantly different from placebo. Testing will continue by comparing the unadjusted p-value to 0.05 for the last LEVI-04 dose level versus placebo. This procedure preserves the global type 1 error. Adjusted p-values from the stepdown Dunnett may not be smaller than the smallest adjusted p-value reported from the previous step. If the smallest Dunnett adjusted p-value from one of the steps is smaller than the previous step's adjusted p-value, then the p-value from the current step will be set to the previous step's adjusted p-value. Dunnett adjustments to the p-values will be calculated using the SAS® PROBMC function. In the first step, for each of the three comparisons, the Z from the associated combination test will be utilized by the PROBMC function as follows to calculate the adjusted pvalue:

$$adj_p3 = 1 - PROBMC("DUNNETT2", max_abs_z, ., ., 3, lam1, lam2, lam3);$$

where,

 $max_abs_z = Maximum of the absolute value of all three combination Z-statistics$

n0 = n01 + n02: placebo sample size at the end of the study

n1 = n11 + n12: LEVI-04 0.3 mg/kg sample size at the end of the study

n2 = n21 + n22: LEVI-04 1.0 mg/kg sample size at the end of the study

n3 = n31 + n32: LEVI-04 2.0 mg/kg sample size at the end of the study

where nij is the sample size of the ith group (i=0,1,2,3) at the interim (j=1) and post interim (j=2) periods.

$$lam1_{-1} = \sqrt{\frac{n11}{n11 + n01}}$$

$$lam2_{-1} = \sqrt{\frac{n21}{n21 + n01}}$$

$$lam3_{-1} = \sqrt{\frac{n31}{n31 + n01}}$$

$$lam1_{-2} = \sqrt{\frac{n12}{n12 + n02}}$$

LEVI-04-21-02 Statistical Analysis Plan	Version: Final 3.0
Date: 18-Mar-2024	Page 21 of 34

$$lam2_2 = \sqrt{\frac{n22}{n22 + n02}}$$

$$lam3_2 = \sqrt{\frac{n32}{n32 + n02}}$$

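### SAP section 7, step 4: with Λ the lower Cholesky factor of Σ, Λ'X + Δ does not have correlation matrix Σ, so conditional power programmed as written depends on how the doses are numbered

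*SAP*

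**What the plan says.** Under Conditional Power Calculations in SAP section 7, the post-interim test statistics for the three dose-versus-placebo comparisons are simulated. The entries of Σ are products λiλj, with λi the square root of ni1/(ni1 + n01). Step 4 then says: "Let Λ be a lower triangular matrix from the Cholesky decomposition of Σ". X is a vector of three independent standard normals. The simulated vector is introduced with "Then $\Lambda'X + \Delta = Z_2 = (Z_{2,2})$ is a three-dimensional" and described as a "vector of normal random variables, with a correlation matrix Σ".

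Step 5 combines each simulated value with the fixed interim Z, using weights √½ and √½, and compares the absolute value with C ≈ 2.349. Step 6 takes the rejection proportion over 5,000 vectors as the conditional power.

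Both methods use these steps, Method 1 with Week 17 effects and Method 2 with Week 5 effects. Each works from the imputed data sets; for Method 1 the SAP says "The conditional power will be calculated based on these multiple imputations interim Week 17 effect sizes". The groups are numbered by dose in section 4.11: group 1 is 0.3 mg/kg, and for group 3 the text is "n3 = n31 + n32: LEVI-04 2.0 mg/kg sample size at the end of the study".

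**The concern.** The three parts of step 4 (lower factor, transpose, correlation Σ) cannot all be true under the usual decomposition Σ = ΛΛ'. Code that follows the formula would give the three comparisons unequal variances and the wrong correlations. The probability that at least one dose is significant should not depend on dose labels, but the literal formula makes it do so.

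Conditional power is what the interim uses to choose between 416 and 624 participants. Because both methods run through step 4, reporting the larger of their two sample sizes does not guard against an error they share. The sponsor would not see it either: "The only recommendation communicated to Levicept will be whether the sample size will need to increase or stay the same".

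**Working it through.** **Inputs.** 1:1:1:1 allocation (SAP 4.2). 208 participants at the interim, so n1 = 52 per arm, and a final N of 416 or 624, so n2 = 52 or 104 per arm after the interim (SAP 7). Weights √½ and √½ (SAP 4.4). Effect scenarios 10/7.5/5, 10/5/2.5 and 10/0/0 with SD 19.2 (SAP 4.3). The interim Z values below are illustrative, since the documents give none.

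**The plan's own figure.** For equal arms λ = √½ and every correlation is 0.5. Solving P(max|Z| ≤ C) = 0.95 gives C = 2.3490, or 0.0188 two-sided per comparison. Both match the SAP, so the set-up is read correctly.

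**The algebra.** Since Cov(X) = I, Cov(ΛX) = ΛΛ' and Cov(Λ'X) = Λ'Λ. With all correlations 0.5:

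- Λ has rows (1, 0, 0), (0.5, 0.866, 0) and (0.5, 0.289, 0.816).
- ΛΛ' has 1 on the diagonal and 0.5 elsewhere, which is Σ.
- Λ'Λ has rows (1.500, 0.577, 0.408), (0.577, 0.833, 0.236) and (0.408, 0.236, 0.667).

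So Λ'X has variances 1.50, 0.83 and 0.67. Its correlations are 0.52 (1,2), 0.41 (1,3) and 0.32 (2,3). The mismatch arises for any non-diagonal Σ, so it does not depend on equal arms.

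**A hand check.** Steps 2 and 4 give Δi = Zi1 × √(n2/n1) for equal arms. At N=416, Δi = Zi1. A dose with interim Z = 2 is significant in the expected direction when √½ × 2 + √½ × (2 + sX) > 2.349, that is when sX > 3.322 − 4 = −0.678, where s is the simulated SD. For that dose alone:

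- s = 1 (correct): Φ(0.678) = 75.1%.
- s = √1.5 (numbered first): Φ(0.678/1.225) = 71.0%.
- s = √0.667 (numbered third): Φ(0.678/0.816) = 79.7%.

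The full simulations below add the small contribution of the other two doses.

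**Full simulation of steps 4 to 6** (at least 1,000,000 draws per case; gap = literal minus correct):

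| N | Interim Z (groups 1, 2, 3) | Correct, ΛX | Literal, Λ'X | Gap (points) |
|---|---|---|---|---|
| 416 | (1, 1.5, 2) | 78.9% | 84.2% | +5.3 |
| 416 | (2, 1.5, 1) | 78.9% | 75.4% | −3.5 |
| 416 | (2, 0, 0) | 75.2% | 71.0% | −4.2 |
| 416 | (0, 0, 2) | 75.2% | 79.9% | +4.7 |
| 416 | (1, 0, 0) | 9.4% | 14.1% | +4.7 |
| 416 | (0, 0, 1) | 9.4% | 5.8% | −3.6 |
| 624 | (1.8, 0, 0) | 84.8% | 79.9% | −4.9 |
| 624 | (0, 0, 1.8) | 84.8% | 89.7% | +4.9 |

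Relabelling one effective dose therefore moves the literal result by up to 9.8 points (89.7 − 79.9, the N=624 rows), while the correct result stays fixed. With one dose leading and the others at 0, the sign changes near 50% conditional power. At N=416 that is near Z = 3.322/2 = 1.66, where the drift just meets the bound and the SD has no effect. The bias is thus neither always upward nor always downward.

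**Typical size.** 1,500 interims were simulated for each of the three SAP scenarios and their reverses (no dropout, one Z vector per interim). The mean absolute gap is 1.0 to 1.7 points at N=416 and 0.6 to 1.0 at N=624, with a 95th percentile of 3.5 to 4.9. With all three interim Z values at or above 0, the gap stays between −4.9 and +5.3. Gaps near 7 points need doses pulling in opposite directions, for example (0, −1, 1) at N=624: 35.8% correct, 28.6% literal.

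**Averaging over imputations.** This shrinks the gap. For assumed between-imputation SDs of Z of 0, 0.15, 0.3, 0.6 and 1.0 (not in the documents), the gap at N=416 for (1, 1.5, 2) falls from +5.3 to +4.7, +3.7, +1.9 and +1.1. For (2, 0, 0) it goes from −4.2 to −3.8, −3.1, −2.1 and −1.1. Method 1 would be expected to shrink more than Method 2, because Protocol 10.1 foresees that only "approximately 80 have completed the Week 17 visit" out of 208; that comparison was not calculated.

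**For scale.** The Monte Carlo standard error of one 5,000-vector run at 75% is √(0.75 × 0.25/5000) = 0.6 points.

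**The case against.** The strongest reply is that this is a slip of one word or one symbol, not a wrong method. The SAP states the target, correlation Σ, and a programmer can check against it. Λ'X is right if lower should read upper, or under a reverse factorisation with Λ'Λ = Σ. Nothing shows that the literal form was programmed. The formulas around step 4 are also damaged in the text as read, and the point turns on one prime. All of this stands, and it is why every figure above is conditional on literal programming. But the word lower is plain prose, the prime is legible, nothing suggests it is an artefact, and the SAP states neither alternative factorisation.

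It is also true that the harm is bounded. The final combination test, C, the type I error and the power table do not use Λ. Typical gaps are one or two points, and equal interim effects give small ones, such as 62.2% correct against 63.7% literal for (1.5, 1.5, 1.5) at N=416. Reporting the larger sample size helps when only one method errs downward. It does not help when both do, and it does not prevent an unneeded increase.

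**Conclusion.** The concern holds: step 4 is internally inconsistent as written. If it was programmed literally, conditional power is wrong by about 1 to 2 points on average at N=416 under the SAP's scenarios, and by up to about 5 points when all doses are at or above placebo. Averaging over imputations reduces this. The direction depends on dose order and on the level of conditional power, so the error cannot be called conservative. With effects rising with dose, as in (1, 1.5, 2), it overstates conditional power and argues against an increase.

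The result rests on the standard reading Σ = ΛΛ', on the prime being present in the original SAP and, for the sizes, on equal arms and the illustrative interim Z values. The SAP states no conditional-power cut-off, so a changed decision can be neither shown nor excluded. This should be corrected, but it does not threaten the validity of the final inference.

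**What to change.** Check the prime in the original SAP. If it is there, replace Λ'X by ΛX in step 4, or define Λ as the upper triangular factor with Λ'Λ = Σ. Then confirm what was programmed: the simulated vectors, less Δ, should have unit variances and correlation Σ, and permuting the dose labels should leave conditional power unchanged apart from simulation error. Rerun the interim conditional power only if the literal form was used.

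The cost is one symbol or one word in the SAP, a one-line program check, and possibly one rerun.
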